18.8. Sponsors reporting responsibilities

It is the responsibility of sponsor to ensure that the following are reported to national competent authorities and ethics committees immediately, but no later than 7 calendar days following the date of awareness by sponsor.

- All serious adverse events.
- All serious device effects.
- All device deficiencies that could have led to serious adverse events but did not because suitable action was taken, intervention had been made or because of fortunate circumstances.
- New findings and/or updates in relation to already reported events.

If the serious adverse event results in imminent risk of death, serious injury, or serious illness that requires prompt remedial action for other subjects, users or other persons or a new finding to such a serious adverse event, sponsor must immediately but no later than 2 calendar days after awareness by sponsor report the event to national regulatory authorities.

19. Suspension or premature termination of the clinical investigation

Sponsor may suspend or prematurely terminate an investigation site or the entire clinical investigation for documented significant reasons.

If a suspicion of an unacceptable risk to subjects develops during the clinical investigation, sponsor will suspend the investigation while the risk is assessed. Sponsor will terminate the investigation if an unacceptable risk is confirmed. Sponsor will ensure that the premature termination will be justified in writing and will promptly inform the regulatory authorities and relevant EC(s). If monitoring or auditing of the clinical investigation identifies serious or repeated deviations at one of the participating investigation sites, sponsor will suspend or terminate the particular investigation site. The sponsor or investigator will inform the regulatory authority as appropriate and notify the EC about the termination of the site.

If suspension or termination of the clinical investigation occurs, the investigator(s) will promptly inform the enrolled subjects. Sponsor will provide resources to fulfil the obligations from the CIP for follow-up on the subjects as necessary.

20. Clinical investigation report

At completion of the investigation, sponsor is responsible for writing the clinical investigation report. The report is retained on file. The report contains a critical evaluation of all data, which have been collected during the investigation. The report describes the methodology and design and a data analysis, including statistical preparation and conclusion.

Sponsor and coordinating investigator must sign the final version of the clinical investigation report or an affidavit, indicating their agreement with the contents. If no coordinating investigator is appointed, then the signatures of the principal investigator(s) should be obtained.

Clinical Manager has the responsibility to submit the approved clinical investigation report EC and regulatory authorities within a year after completion of the investigation.

21. Publication policy

Publication policy is specified in Sponsor Investigator Agreement.

23.1. Appendix 1 – Quality of life questionnaire

This questionnaire asks you about the use of the stoma appliance from this test period and your experiences. You will be asked questions about the discreetness of the stoma appliance, comfort relating to wearing the stoma appliance, confidence you have with the stoma appliance, and how the device impacts your social life.

Please think about your experience with using the stoma appliance **during the past seven days** and please select the box that is closest to your current situation. There are no right or wrong answers. We want to understand how beneficial you think the stoma appliance is and also what problems you may have experienced with it.

For each of the statements, think about how the specific issue affects you. Please answer **ALL** questions as honestly as you can, and **please remember to answer the questions in relation to the past seven days only.**

Discreetness 1. It was difficult to hide the stoma appliance under clothing 2. I was self-conscious about the appearance of the stoma appliance 3. The stoma appliance limited the choice of clothes that I could wear 4. The stoma appliance was obvious to other people 5. The color of the stoma appliance was discreet 6. It was difficult to hide the stoma appliance because of ballooning	Confidence 1. I was confident that the stoma appliance would not leak 2. I worried that the stoma appliance would become loose from my body 3. I felt confident that I could spend the night away from home despite wearing the stoma appliance 4. I was confident the stoma appliance would not cause any problems for me 5. I felt confident to take part in physical activities (for example, sports) whilst wearing the stoma appliance 6. I worried that the stoma appliance would make a rustling noise.
Comfort 1. The stoma appliance was comfortable to wear 2. I was not concerned about skin irritation under the stoma appliance (for example, feelings of burning, itching, pinching or pain) 3. It was uncomfortable to remove the stoma appliance from my body 4. I often forgot that I was wearing the stoma appliance 5. The stoma appliance was comfortable as it fitted well to my body 6. The stoma appliance disrupted my sleep during the night	Social life 1. I worried that my family and friends felt awkward around me because of the stoma appliance 2. I felt my social life had been restricted because of the stoma appliance 3. I avoided close physical contact with family and friends because of the stoma appliance 4. I worried about whether I could have a relationship because of my stoma appliance 5. I worried about whether the stoma appliance would affect my sex life

23.2. Appendix 2 – Leakage scale questionnaire (OLI)

Emotional impact

When you thought about your ostomy device and the risk of leakage, what emotions did you feel?

In the last 7 days, due to leakage or worry about leakage...	All of the time	Often	Sometimes	Rarely or never
1. I felt panic	0	1	2	3
2. I felt stressed out	0	1	2	3
3. I felt more afraid about leaks in the future	0	1	2	3
4. I felt worry	0	1	2	3
5. I felt frustrated	0	1	2	3
6. I felt embarrassed	0	1	2	3
7. I felt worried that I might leak	0	1	2	3
8. I couldn't sleep	0	1	2	3
9. I kept waking up at night to check my stoma	0	1	2	3
10. I kept checking my ostomy bag to see if I have leaked	0	1	2	3

Usual and Social activities

When you thought about your ostomy device and the risk of leakage, how did it affect your activities?

In the last 7 days due to leakage or worry about leakage...	All of the time	Often	Sometimes	Rarely or never	Not applicable
11. I decided to stay at home	0	1	2	3	9
12. I couldn't do light activities	0	1	2	3	9
13. I changed my plans	0	1	2	3	9
14. I was unable to go out and meet family and friends	0	1	2	3	9
15. I avoided close physical contact with family and friends	0	1	2	3	9
16. I did not want to see people	0	1	2	3	9
17. I avoided people	0	1	2	3	9
18. I tried to avoid meeting new people	0	1	2	3	9

Coping and in control

When you thought about your ostomy device and the risk of leakage, how did it affect your ability to cope?

In the last 7 days, due to leakage or worry about leakage...	All of the time	Often	Sometimes	Rarely or never
19. I felt in control	0	1	2	3
20. I was able to cope	0	1	2	3
21. I felt calm	0	1	2	3
22. I saw my friends as I usually do	0	1	2	3

23.3. Appendix 3 - Bristol scale

Type 1	Type 2	Type 3	Type 4	Type 5	Type 6	Type 7
						

Leeds S, Fletcher RW (1997) "Stool form scale as a useful guide to intestinal transit time" Scand J Gastroenterol. 32 (9) 929-4

23.4. Appendix 4 – Questions

Assessment/endpoint	Question	Answer
Assessment		
Reason for change	What is the reason for change? Please tick ALL that apply.	
 • I follow my usual changing pattern • There is leakage under and outside the baseplate (soiling the clothes) • Due to a notification from the App • The entire baseplate is detached • The outer edge of the baseplate is detached • The center of the baseplate is detached • I am afraid the baseplate will detach • The area around the stoma is itching • The area around the stoma is painful • There is leakage under the baseplate (but not outside the baseplate) • The stoma bag is filled with air • There is a vacuum in the stoma bag • Other
Secondary endpoint(s)		
Frequency of leakage onto clothes	Think back on the last 3 weeks - how many times have you experienced leakage onto clothes?	Number
Overall experience of leakage onto clothes with test product compared to only using usual product	Compared with your usual product, to which degree have you experienced leakage onto your clothes with test product?	Fewer episodes of leakage onto clothes - More episodes of leakage onto clothes
Reliability of notifications	To which degree did you find the notifications from the App reliable and trustworthy?	Very high degree - High degree - Some degree - Low degree - Not at all
Ability to move with test product	Compared to your usual product, how was your freedom to move with test product?	Much better - better - Same - Worse - Much worse
Users worry of leakage	Think back on the last 3 weeks - to which degree have you worried about leakage?	Very high degree - High degree - Some degree - Low degree - Very low degree/Not at all

Confidence to avoid leakage onto clothes with test product compared to only using usual product	Compared to your usual product, did you feel confident that you could avoid leakage onto clothes?	Yes – No
Confidence in daily life compared to only using usual product	Compared to your usual product, to which degree did the test product give you confidence in daily life?	Much higher degree- Higher degree- Same degree - Lower degree- Much lower degree
Feeling of control with test product compared to only using usual product	Compared to your usual product, did test product give you a feeling of leakage control?	Yes, higher leakage control No, lower leakage control
Control of leakage progression with test product compared to only using usual product	Compared to your usual product, did the test product give you a feeling of control of leakage progression?	Yes, higher control of leakage progression No, lower control of leakage progression
Feeling of security with test product compared to only using usual product	Compared to your usual product, did you feel more or less secure with test product?	I felt more secure – I felt less secure
Evaluation of confidence to increase social activities with test product compared to only using usual product	Compared with your usual product, did the test product affect your confidence to engage in social activities such as seeing friends, and do physical activities?	I felt more confident - I felt less confident
Evaluation of sleep with test product compared to only using usual product	Compared with your usual product, did the test product affect your sleep?	Yes, to the better Yes, to the worse No, the same
Confidence at night with test product compared to only using usual product	Compared with your usual product, to which degree did the test product give you confidence at night?	Much higher - Higher - Same - Lower - Much lower
Preference	Which product solution do you prefer?	Own product - Own product with test product
Reason for preference	What is your reason for preference? (Please tick all that apply)	
 • Body fit • Ability to bend and stretch • Feeling of security • Feeling of confidence • Less fear of leakage onto clothes

		
 • Discreet to wear • Discreteness in leakage control • Better sleep • Less embarrassment • Other text
Preference	How often would you use the test product?	Will never use it – Will use it rarely – Will use it sometimes – Will use it often – Will use it every day
Preference	If the test product was available today, would you start using it?	Yes – No
Preference	Would you recommend the product to others living with a stoma?	Yes – No
Evaluation of users' peace of mind with test product	To which degree did the test product give you peace of mind?	Very high degree- High degree- Low degree- Very low degree
To evaluate users' assessment of QoL with test product compared to usual product	Overall, do you think the test product can improve your feeling of control and confidence to avoid leakage onto clothes and therefore improve your quality of life?	Yes - No => if no, why not? Text
Adhesive residue to skin	To which degree did you experience adhesive residue to the skin in the area around the transmitter?	Very low degree/Not at all - Low degree - Some degree – High degree -Very high degree
Adhesive residue to transmitter	To which degree did you experience adhesive residue on the backside of the transmitter?	Very low degree/Not at all - Low degree - Some degree – High degree -Very high degree
Exploratory endpoints		
HRQoL evaluation		See Appendix 1
OLI evaluation		See Appendix 2

Evaluation of self-management (predictability of change) of stoma appliance compared to usual product	To which degree does test product support you to control the daily routines around appliance change?	Very high degree - High degree - Some degree - Low degree - Very low degree / Not at all
Evaluation of self-management (predictability of change) of stoma appliance compared to usual product	To which degree does test product make it easier to know when to change appliance compared to own product?	Very high degree - High degree - Some degree - Low degree - Very low degree / Not at all

Signature Page for VV-0308987 v2.0

Approved	[Redacted]	29-Mar-2021 12:03:16 GMT+0000
Approved	[Redacted]	29-Mar-2021 13:35:22 GMT+0000
Approved	[Redacted] Medical / Clinical	29-Mar-2021 13:39:23 GMT+0000
Approved	[Redacted] Medical / Clinical	29-Mar-2021 14:56:10 GMT+0000

Signature Page for VV-0308987 v2.0

Document Owner: [Redacted]

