5.3. Secondary endpoints

Secondary endpoints:

- Frequency of leakage onto clothes before and after use of test product
- Experience of leakage onto clothes compared to only using usual product
- Reliability of notifications
- Ability to move with test product
- Subjects worry of leakage before and after use of test product
- Confidence to avoid full leakage with test product compared to only using usual product
- Confidence in daily life compared to only using usual product
- Feeling of control with test product compared to only using usual product
- Control of leakage progression with test product compared to only using usual product
- Feeling of security with test product compared to only using usual product
- Evaluation of confidence to increase social activities with test product compared to only using usual product
- Evaluation of sleep with test product compared to only using usual product
- Confidence at night with test product compared to only using usual product
- Evaluation of users' preference
- Reason for preference
- Evaluation of users' peace of mind with test product
- To evaluate users' assessment of QoL with test product compared to usual product
- Adhesive residue to transmitter

- Adhesive residue to skin

Explorative endpoints:

- Change in HRQoL, Appendix 1
- Change in Ostomy Leakage Impact (OLI), Appendix 2
- Evaluation of self-management (predictability of change) of stoma appliance compared to usual product

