6.1.1. Inclusion criteria

Inclusion criteria:	Inclusion:

1. Have given written informed consent
 
2. Be at least 18 years of age and have full legal capacity
 
3. Have had a stoma for more than three months
 
4. Have intact skin on the area used in the evaluation meaning no broken skin and only minor discoloration of the skin (assessed by investigator)
 
5. Be able to use one of the five test products (i.e. Ø40, Ø50, Ø60, Ø70, Ø80 mm)
 
6. Ileo- or colostomists with liquid output (Bristol scale type 6-7).
 
7. Currently using a Coloplast product (1pc/2pc Flat/Convex/Concave) from e.g Assura/Sen-Sura/SenSura Mio
 
8. Have self-reported problems with leakage* (three times within 14 days)
 
9. Have worry of leakage 'to some, high or very high degree'
 
10. Is familiar with the use of a smartphone
 
*Leakage: Leakage is defined as output from the stoma on the backside of the baseplate (underneath the baseplate)
	
1. To meet the Helsinki Declaration
 
2. To meet the Helsinki Declaration
 
3. Recovered from ostomy surgery
 
4. The skin must be intact, otherwise the product will change classification category.
 
5. The technical design of the device requires use of one of the five sizes
 
6. The technical design of the device requires liquid output
 
7. To minimize unknown factors from competitor adhesives, only users of Coloplast products can be enrolled in this study.
 
8. The sensors in the product will only be activated by moist/leakage so in order to be able to evaluate the product the subjects need to have a certain amount of leakage.
 
9. Users who do not worry of leakage at any or low degree are excluded.
 
10. Users who do not know how to maneuver a smartphone will have to large difficulties in using the product and will also not be able to use the product going forward as it requires that the user has a smartphone.

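### The comparative item on leakage onto clothes prints only Fewer and More, so subjects with no change have no true answer, and section 10.1 does not say how to score them

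*Combined protocol and SAP*

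**What the plan says.** Section 5.3 lists the secondary endpoint "Experience of leakage onto clothes compared to only using usual product". The flow chart in section 7.2 has the subject answer it once, at Visit 2. Appendix 4 gives the answers as "Fewer episodes of leakage onto clothes - More episodes of leakage onto clothes". Nothing is printed between or beside these two phrases.

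Other Appendix 4 items do offer a neutral answer. The item on freedom to move reads "Much better - better - Same - Worse - Much worse", and the sleep item has a third answer for no change. Section 5.4 says that user-experience items are either five-point scales or yes/no.

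Entry criterion 8 (section 6.1.1) is "Have self-reported problems with leakage* (three times within 14 days", with the footnote "Leakage is defined as output from the stoma on the backside of the baseplate (underneath the baseplate". Criterion 9 concerns worry only: "Have worry of leakage 'to some, high or very high degree". No criterion requires a leak to have reached the clothes. Appendix 4 treats the two events as different: among the reasons for change, "There is leakage under the baseplate (but not outside the baseplate" is listed apart from leakage that soils the clothes.

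A separate item, asked at Visits 1 and 2, takes a count: "Think back on the last 3 weeks - how many times have you experienced leakage onto clothes". Section 10.1 puts it in a paired Poisson model.

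For yes/no items, section 10.1 gives an exact binomial interval and a test against 50% at the 5% level. Five-point items can be grouped into favourable answers versus all others and handled in the same way. Invalid data points may be omitted. There is no rule for a subject with no episodes or an unchanged number.

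**The concern.** Two kinds of subject can be enrolled and then have no true answer: those with no leakage onto clothes with either product, and those with the same non-zero number of episodes. As printed, the item makes them pick a direction or leave it blank.

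A subject who had no clothes leakage during the test period may well choose Fewer although nothing improved. Others may guess or skip. The reported proportion then mixes real change with the effect of a missing answer, and the denominator is left to judgement after the answers are in.

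The study is open-label with one arm, and section 10.4 allows its results to support claims. A statement that a given share of users had fewer leaks onto clothes is a natural candidate for such a claim.

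**Working it through.** **1. Can no-change subjects be enrolled?** Criterion 8 is met by output under the baseplate, criterion 9 by worry. The reason-for-change list recognises leakage that stays under the baseplate, and the count item accepts 0 at both visits. So the criteria admit them. The documents do not say how many to expect.

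**2. The hurdle, if section 10.1 is applied to this item.** The plan states no figure to reproduce (no power, no sample size calculation). Inputs: n = 25 (sections 6 and 10.2), null 50%, 5% level, taken as two-sided.
- P(X ≥ 18 | 25, 0.5) = 0.0216; doubled, 0.043.
- 17 of 25 gives 0.108, so at least 18 (72%) are needed.

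**3. Effect of k no-change subjects.** Two assumed behaviours:
- (a) All k choose Fewer and the other 25 − k are truly 50:50. The chance of a favourable significant result is P(Bin(25 − k, 0.5) ≥ 18 − k). For k = 5 this is P(Bin(20, 0.5) ≥ 13) = 0.132. The expected share of Fewer is (5 + 10)/25 = 60%, not 50%.
- (b) The k guess at random and the others choose Fewer with an assumed probability of 80%. For k = 5 the expected share is (2.5 + 16)/25 = 74%, not 80%.

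| k | (a) favourable significant result, no true effect | (b) power with guessing |
|---|---|---|
| 0 | 2.2% | 89% |
| 3 | 6.7% | 79% |
| 5 | 13.2% | 69% |
| 8 | 31.5% | 53% |
| 10 | 50.0% | 42% |

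**4. How large might k be?** Only an assumed range is possible. Three leaks in 14 days is 3/14 × 21 = 4.5 per three weeks. Let q be the share of leaks reaching the clothes (not in the documents). With independent Poisson counts and no device effect, P(zero in both periods) = exp(−2 × 4.5 × q) = exp(−9q). Equal counts of any size come from the same model.

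| q | zero in both, of 25 | equal counts (including zero), of 25 |
|---|---|---|
| 0.1 | about 10 | about 12 |
| 0.2 | about 4 | about 8 |
| 0.3 | about 2 | 6 to 7 |
| 0.5 | 0.3 | about 5 |

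The rate of 4.5 is the entry threshold, not an expected mean. If the mean were double, q = 0.2 would give exp(−3.6) = 2.7% with zero in both periods, against 16.5% at 4.5. The second column shows that the gap is not confined to subjects with no leaks: at q = 0.2 about half of the ties have a non-zero count.

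**The case against.** **The two phrases may be the ends of a five-point scale.** The stem asks for a degree, each of the nine other Appendix 4 items with that stem has four or five answers, and section 5.4 allows only five-point or yes/no formats. A midpoint would then exist, and grouping favourable answers against all others would count it as not favourable. This is possible, but the other five-point items print every point and this one does not. The plan should settle it.

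**A reader might infer that subjects with zero counts at both visits cannot truthfully answer Fewer and should be excluded.** The documents do not support that. The three-week window belongs to the count item; the comparative item has none. Subjects have had a stoma for more than three months, so someone who leaked onto clothes earlier, but not in the three weeks before Visit 1, can validly answer Fewer. Exclusion on the counts could override true answers.

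**A reader might infer that the proportion will be biased upwards.** That needs these subjects to lean to Fewer. If they guess, the effect is dilution. The test against 50% is itself inferred, because the item as printed is neither yes/no nor five-point.

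**A reader might infer that criterion 8 is wrong.** Its stated reason is that sensors respond only to moisture or leakage, which suits the primary endpoint. The gap lies in the answer list.

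It also stands that this is one of 19 secondary endpoints in an exploratory study, and that clothes leakage is separately measured by counts. Some other items, such as leakage control and security, are forced choices too. Even so, none of this gives a no-change subject a true answer to this item.

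**Conclusion.** The point holds as a minor one. The printed answers leave out no change, the entry criteria admit subjects to whom that applies, and section 10.1 has no scoring rule for them. The text shows this without any calculation.

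Size and direction are illustrative. They rest on an assumed number of no-change subjects, on how those subjects would answer, and on the test against 50% being used. With five such subjects, the chance of a favourable significant result without any effect rises from 2.2% to 13% if all choose Fewer; power at an assumed 80% falls from 89% to 69% if they guess. If most leaks reach the clothes, few subjects will have zero in both periods, but equal non-zero counts remain. The primary endpoint, which is judged from pictures of the baseplate, is unaffected.

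**What to change.** **If the app can be edited:** add two answers to the item, *Same number of episodes* and *No leakage onto clothes with either*. If a five-point scale is intended, print all five points with the neutral midpoint. State in section 10.1 that neutral answers stay in the denominator as not favourable, following the grouping that section already describes for five-point items.

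**If it cannot:** keep the answers as given in the main result. Add a sensitivity analysis in which subjects whose Visit 1 and Visit 2 clothes-leakage counts are equal, including zero at both, do not count as Fewer, and report how many there are. Do not drop them from the main result on the counts alone.

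**Cost:** one or two app answers and a sentence in section 10.1, or one extra analysis from data already collected. The proportion becomes less favourable and 72% harder to reach. With five neutral answers and 80% Fewer among the other 20, the expected share is 16/25 = 64%, and the chance of reaching 18 is 21%, against 89% with no neutral answers. A share below 50% must then not be read as more leakage, so the Fewer, More and neutral counts should be shown separately.
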